Study Protocol

NCT04175106

Date: 19-Nov-2020

NORTH CAROLINA STATE UNIVERSITY
INSTITUTIONAL REVIEW BOARD FOR THE USE OF HUMAN SUBJECTS IN RESEARCH
SUBMISSION FOR NEW STUDIES

Protocol Number 19138

Project Title

CLOSED - Establishing optimal nutritional quality of blueberries: a proof of concept study to improve the nutritional quality of the average diet using common plant breeding and processing practices.

IRB File Number:

Original Approval Date:

09/24/2019

Approval Period

07/29/2021 - 01/01/2100

Source of funding (provide name of funder not account number):

Foundation for Food and Agriculture Research

NCSU Faculty point of contact for this protocol: NB: only this person has authority to submit the protocol

[name]: Kannapolis Research

Does any investigator associated with this project have a significant financial interest in, or other conflict of interest involving, the sponsor of this project? (Answer No if this project is not sponsored)

No

Is this conflict managed with a written management plan, and is the management plan being properly followed?

No

Preliminary Review Determination

Category:

Full Board - Closed

In lay language, briefly describe the purpose of the proposed research and why it is important. Provide a brief synopsis of the study including who is targeted to participate and the data collection methods employed (limit text to 1500 characters)

The 4-phase crossover study focuses on within participant variation in the clearance kinetics of (poly)phenols in 2 different commercial blueberry varieties, a minimally processed blueberry-rich protein bar, and a control beverage of matched-nutritive content in healthy human volunteers to identify the impact of berry content and processing on absorption and elimination kinetics. Sex will be used as a covariate in statistical analysis and as within participant variation is the primary outcome, population diversity is not required. There is no attempt to recruit or limit or stratify by socioeconomic statuses. We will establish clearance in blood and urine over a 48-hour period across 4 treatment phases. The entire study will last 3-months involving a consent visit, screening visit, four weeks of restricted food intake, four visits of 9.5 hours in the clinic, and additional 8 visits that will take 1 hour each. The total study requires a total commitment of 54.5 hours over the 3 month enrollment period.

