been used by PHHI extensions for over 5 years now. Further planned recruitment through use of local newspapers and Magazines (Cabarrus County Magazine, Salisbury County Magazine) rounds out this recruitment strategy, if required. As the studies primary purpose is to establish the difference in bioaccessibility of blueberries in healthy, middle age individuals, we feel we have gone above and beyond attempting to be as inclusive as possible for a study requiring less than 30 individuals and not controlling for ethnic diversity or genetic differences in metabolism. We expect we will hit our recruitment target within weeks of posting the initial flyers and will therefore use a phased advertisement approach to avoid unnecessary expression of interest. Recruitment will be made on a first approached basis, provided eligibility criteria are met and having equal distribution of male and female participants.

Detailed Strategy:

Study recruitment will be conducted via posting flyers (Annexes 1A and 1B) on pre-approved bulletin boards on the NCRC buildings, NCRC public listservs; postings with the Parish Nurses at Carolina HealthCare System (Atrium Health) and "Faith Community Health Ministry"; posting on local public bulletin boards: West Cabarrus YMCA, Harrisburg YMCA, Kannapolis YMCA, South Rowan - J. Fred Corriher Jr. YMCA, Salisbury - J. F. Hurley YMCA, Rowan Public Library-Headquarters, South Rowan Regional Library, Concord Library, Harrisburg Library, Kannapolis Library, Mt. Pleasant Library; Extensions and Health Alliances: Cabarrus Health Alliance, Rowan County Health Department, Cabarrus County Extension, Rowan County Extension, eNews at Salisbury Pediatrics; and/or newspapers and local magazines (Annex 1B): Independent Tribune, Salisbury Post, Cabarrus County Magazine, Salisbury County Magazine.

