The inclusion questionnaire/interview will select the average healthy adult population for analysis of the clearance rate of blueberry components (phytonutrients) through the body over time. Thus, the study will include male and female adults between 25-65 years because there is evidence that adolescence and the elderly have different metabolic processes (particularly differing absorption and metabolism) compared to this age range; non-smokers, non-tobacco users [no vaping or dipping (tobacco chewing)], or who ceased it \geq 6 months ago because it is known to affect metabolic processes; who present no allergies to fruits or vegetables containing polyphenolic (e.g. anthocyanins, flavonoids) and phenolic acids such as blueberries, red apple, strawberry, red orange, purple onion and broccoli because participants will be served blueberries; who present no allergies to whey protein or salicylates because participants will be served with blueberries, which contain traces of salicylates, and the blueberry-rich protein bar containing whey protein; who are generally healthy and without chronic diseases including cancer, type 1 and 2 diabetes; who are not prescribed thyroid or hypoglycemic medication or hormone replacement therapy (HRT) (due to the likely concomitant effects that these medications cause on the primary endpoint in the trial), otherwise, it can impact physiological processes associated with digestion and absorption; who has not been consuming any phytonutrient-containing supplements (e.g. with berry, cocoa, coffee or tea extracts) for at least a month before the study and willing to not consume it during the study, otherwise, it would interfere with the analysis of the phytonutrients after consumption of the treatments for this study; who lives within 40 miles from the NCRC campus to avoid drop-outs due to traffic and the required early morning visits; those agreeing to restrict dietary intake of rich sources of phytonutrients targeted on the study (Annex 9) during the wash-out and clinical sampling periods, agreeing to comply with study procedures involving the collection of urine and blood samples, and to record their additional dietary intake over 2 days before each feeding visit, and two days after the intake of the blueberries or blueberry product, otherwise, this study would not be suitable for them. The clinical screening will enroll/include those who have BMI ≥ 18.5 and ≥ 30 (lbs/in² x 703) and a successful (i.e., within normal range for healthy individuals) biochemical, hematological and urine analyses assessed by the clinical advisor, as the design of the study is to establish bioequivalence in healthy middle aged humans and unhealthy, or adolescence or the elderly have altered absorption and metabolism. Studying these groups would require considerably higher participant numbers, which will be the focus of future investigations.

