There is no intent to make a claim about the impact of a nutritional product on a diagnosis, cure, mitigation, treatment, or prevention of a disease or health related condition. Only clearance kinetics are being explored in the present trial. Amendment COVID-19: the consent visit will occur in room 1308 of the UNC-CH Human Research Core clinical suite, on the North Carolina Research Campus ([name]) or virtually via the study coordinator's NC State University Zoom account. We will also offer the possibility of reading and signing the consent form online (using electronic signature or emailing us a scanned and signed document) or via mail.

In addition to the normal study procedures stated here, we will also follow all procedures and materials described in the COVID-19 Additional Procedures packet. Once a vaccine is developed to Address COVID-19, we will cease all COVID related procedures and communication and only implement normal study procedures as described in this IRB application.

Amendment request (November/2020): At the consent visit, date of birth is collected by the study coordinator into a password-protected Drive to label blood tubes that are used at the clinical screening and study visits to confirm the identity of each participant during blood draw by our UNC-CH partner's phlebotomists. At the clinical screening, the blood tubes and paperwork that are filled out with the participant's date of birth by phlebotomists are sent to LabCorp.

Are you requesting the use of secondary information to be used as data for this research project? The secondary information can either currently exist or be generated in the future.

Discuss the following: permission to access the information (direct permission from the participant or records release), how researchers will access, transfer, store, and destroy the data.

Discuss the identifiable/re-identifiable nature of the data through either direct IDs, indirect IDs, or triangulation of datasets, data points, researcher access/expertise, or analysis. .

List all data categories to be requested (ex: age, race, student ID, GPA, ACT, Medical ID, diagnosis).

Discuss if the data requires a Data Use Agreement.

Discuss if the data are subject to FERPA, HIPAA, or the GDPR.

No

Social/Reputational?

No

Psychological/Emotional?

No

Financial/Employability?

No

Legal?

No

Physical?

Yes

Academic (affect grades, graduation)?

No

Employment (affect job)?

No

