Data will be reported as an aggregate (mean and standard deviation for groups of participants) of the phytonutrient concentrations in the blood serum and urine and reported across time points post-consumption. There will be no chance of linkage of reported mean and standard deviation concentration data to coded samples or to participantâ€™s identifiers.

Will anyone besides the PI or the research team have access to the data (including completed surveys) from the moment they are collected until they are destroyed? This includes sharing data with sponsors, journals, or using the data for future research endeavors. If you are sharing the data, this should be in your consent form.

No deidentified data will be shared with the study sponsor nor in publications, as participant and study outcome data will only be provided as summarized group means and standard deviations. We will retain volunteerâ€™s name, age, gender, telephone number and email address in a database stored on a secured network in the case where consent is given to be recontacted for future studies.

Describe any compensation that participants will be eligible to receive, including what the compensation is, any eligibility requirements for that compensation, and how that compensation will be delivered. Examples of compensation include: monetary compensation, research credits, raffle/drawing, novel items. Make sure to check with your department regarding issues of tracking payments as your department accounting office may have requirements that affect your human subjects privacy (such as the mandatory tracking of anyone who receives compensation). This tracking may influence the confidentiality/anonymity of your research and must be addressed in this application.

All the subjects of the study per protocol will receive a \$312 maximum compensation (in addition to travel reimbursement) calculated in proportion to the number of collections or food records provided, which is broken down as follows: a 24-hour urine collection is \$5/collection, a blood sample is \$7/sample, the completion of food intake report is \$4/four days (Annex 8 details calculation breakdown by each intervention). This will be calculated at the completion of the study, or upon withdrawal, and includes urine and blood collections, and food intake records. The study coordinator will fill out a form (Annex 8) with all the procedures you have taken.

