1.2 Methodology For Longitudinal Studies

Longitudinal studies involve repeated measurements of specified variables over a period of time. Within each period k , each subject i will undergo 7 blood collections at time points of 0, 1, 3, 6, 9, 24, and 48 hours post-treatment and 5 urine collections at -48, -24 pre-intervention and 0-9, 9-24 and 24-48 hours post-treatment tracking concentrations of pre-specified metabolites reported as concentration versus time. Concentrations will be converted to corresponding pharmacokinetic parameters: maximum serum concentration (C_{max}), time at maximum concentration (T_{max}), the half-life [$t_{1/2}$], the area under the curve (AUC), area under the first moment curve (AUMC), the clearance (CL), the volume of distribution (V_d), and the mean residence time (MRT) of blueberry-derived metabolites in the blood and urine using an appropriate pharmacokinetic model (PK) [BAMStudy2020]. The software Phoenix WinNonlin is planned to be used to fit the PK model. Using the calculated AUC and dosage D, the total bioavailability for each metabolite can be determined [2]. Subject specified covariates (such as gender, age, body mass index, treatment order, and sample type) may be significant in the PK

model and will be considered for potential inclusion. However, the exact nature of this model will be determined as the study is completed and is beyond the scope of this statistical analysis plan.

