1.4 Proposed Methodology for Crossover Longitudinal Studies

The model specified in (1.1) will serve as a framework for testing the differences of fixed effects between treatments. Using the methodology outlined in Section 1.2, the appropriate PK parameters for a given metabolite (ex. Bioavailability) will be calculated. The PK parameters will be represented as the continuous responses Y_{ijkl} in the model. Note that each measured PK parameter is specified to a given subject I receiving treatment j at a specified period k within sequence l .

It is of primary interest to test the potential differences in bioavailability of blueberry-derived metabolites across treatments. Given the number of metabolites being tested, multiple comparison adjustments will be necessary. There are a multitude of strategies for tackling such problems each with their respective advantages and disadvantages. However, given the relatively small sample size ($n=28$), controlling the family-wise error rate (FWER) across all metabolites

may drain requisite statistical power needed to detect any difference between treatments. It may be beneficial to set up a smaller subset of metabolites prior to analysis that are of primary interest and then investigate differences between the remaining metabolites in an exploratory nature.

[figure not shown]
2 Recommended Analysis/Design

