2.3 Interpreting Model Output

Using the lmerTest package in R, we can conduct hypothesis tests for fixed and random effects in linear mixed effects models. The anova function provides F-tests on the fixed effects, letting you evaluate if a fixed effect is useful for explaining the response. Using the above model, the anova output is as follows:

```
> anova(fit)
Type III Analysis of Variance Table with Satterthwaite's method
  Sum Sq Mean Sq NumDF DenDF F value    Pr(>F)
Treatment  158.70 158.70     1 177.99 17.746 4.005e-05 ***
'Visit Period' 391.38 195.69     2 178.34 21.883 3.170e-09 ***
---
Signif. codes:  0 '***' 0.001 '**' 0.01 '*' 0.05 '.' 0.1 ' ' 1
```

Based on this, we can see that both treatment and period are useful for explaining the response. Since treatment is binary (control, treatment) here, we can examine if administering the treatment increases or decreases the response, on average. The summary function is one way to do this. Below is selected output:

```
> summary(fit)
Fixed effects:
  Estimate Std. Error    df t value Pr(>|t|)    
(Intercept)  0.02752  0.84451 4.24374  0.033  0.975
TreatmentTreatment 1.91665  0.45498 177.99167  4.213 4.00e-05 ***
'Visit Period'B -0.29409  0.55514 178.22795 -0.530  0.597
'Visit Period'C  3.24513  0.63618 178.66646  5.101 8.57e-07 ***
```

Notice the estimate for the TreatmentTreatment is 1.91665. This indicates the model the model estimates a 1.91655 increase in AUC if the Treatment is administered instead of the control. The corresponding p-value is small, so we can be confident that the treatment increases AUC, on average. To check if the random effects are useful for explaining the response. Since we are not interested in specific levels of the random effects, we just want to check if considerably variation is coming from the random effects. The ranova function runs a hypothesis testing the variance against zero. For the ANOVA model, here is the output:

```

> ranova(fit)
ANOVA-like table for random-effects: Single term deletions

Model:
AUC48 ~ Treatment + 'Visit Period' + (1 | seq)
      npar  logLik   AIC   LRT Df Pr(>Chisq)
<none>      6 -454.87 921.74
(1 | seq)    5 -460.85 931.70 11.969  1  0.000541 ***
---
Signif. codes:  0 '***' 0.001 '**' 0.01 '*' 0.05 '.' 0.1 ' ' 1

```

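### The eligibility text says the trial is to establish bioequivalence, but the plan tests differences, and the proposed raw-scale models without a subject effect do not estimate product ratios within person

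*Protocol*

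**What the plan says.** The word bioequivalence describes the study's aim in one clause of the protocol's answer on inclusion and exclusion criteria. The clause appears once under inclusion and once under exclusion, and explains why unhealthy people, adolescents and the elderly are left out: "as the design of the study is to establish bioequivalence in healthy middle aged humans".

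Every other statement of aim differs:

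- Protocol, how participants will be found and selected: the "primary purpose is to establish the difference in bioaccessibility of blueberries".
- Protocol, opening synopsis: products are compared "to identify the impact of berry content and processing on absorption and elimination kinetics".
- Protocol, end of the study procedures: "Only clearance kinetics are being explored in the present trial".
- SAP 1.4: "It is of primary interest to test the potential differences in bioavailability of blueberry-derived metabolites" across treatments.

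On analysis, SAP 1.2 derives the pharmacokinetic parameters and adds: "Using the calculated AUC and dosage D, the total bioavailability for each metabolite can be determined". SAP 1.3 gives a general crossover model with a random subject effect nested in sequence. SAP 2.2 then proposes models 2.1 and 2.2 for analysis. Both have sequence, treatment and period terms (2.1 adds treatment by period) and no subject term. The code fits untransformed AUC48 with a random sequence effect only. SAP 2.3 interprets the toy output by F-test and p-value: "The corresponding p-value is small, so we can be confident that the treatment increases AUC, on average".

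**The concern.** A bioequivalence aim and a difference aim need different analyses. Equivalence is shown when a confidence interval for a ratio lies inside limits fixed in advance. A difference test that fails to reject shows nothing of the kind. With the word in the protocol and only difference tests in the SAP, someone could later read a non-significant contrast as evidence that two products are equivalent. The bar against fresh berries is the likeliest place, because step 4 of the procedures makes the bar equal to one serving on total phenolics (789 mg). That is a dose match on one total, not a forecast of equal bioavailability.

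The larger stake lies in the trial's own question: how much variety and processing change bioavailability. A p-value does not show what size of difference remains possible. A raw-scale AUC difference is not a relative effect. A model without a subject term leaves stable person-to-person variation in the error, which gives away much of the benefit of a crossover.

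**Working it through.** **The plan's own figure.** The only sample-size figure is 28 recruited for 24 completers at 15% dropout. 24/0.85 = 28.2 (29 if rounded up); 24 × 1.15 = 27.6, which rounds up to 28; 28 × 0.85 = 23.8. So 28 is consistent with the dropout arithmetic. No alpha, power, effect size, SD or margin supports the 24.

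**Inputs.** From the documents: 24 completers, four periods, four treatments. Assumed, because the documents give none: log scale; within-person CV of 20%, 30%, 40% or 60%; one metabolite and one product pair; two-sided 5% for difference tests; limits 0.80 to 1.25 with 5% per one-sided test for equivalence; no multiplicity adjustment unless stated.

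**Formulas, with a subject effect.** σ_w = √ln(1+CV²). SE of a log ratio = σ_w √(2/24). df = 96 − 1 − 23 − 3 − 3 = 66. At CV 30%: σ_w = √ln(1.09) = 0.2936 and SE = 0.2936 × 0.2887 = 0.0847. The 95% interval factor is exp(1.997 × 0.0847) = 1.18. Power uses the noncentral t for difference tests, and two one-sided tests averaged over the chi-square distribution of the variance for equivalence.

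| Within-person CV | 20% | 30% | 40% | 60% |
|---|---|---|---|---|
| Power to show equivalence, true ratio 1.00 | 97% | 66% | 27% | 0.1% |
| True ratio 0.75 not significant | 0.1% | 8% | 28% | 57% |
| Same, Bonferroni for three contrasts | 0.6% | 18% | 45% | 74% |
| 95% CI: multiply or divide ratio by | 1.12 | 1.18 | 1.25 | 1.38 |

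An 80% benchmark is lost above a CV of about 27% for equivalence and about 36% for detecting the deficit. With all 28 completing, these become about 29% and 39%.

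**What leaving out the subject effect can cost.** Assume a between-person CV of 50%, so σ_b² = ln(1.25) = 0.2231, and let the sequence term absorb none of it. The model's SE becomes √(2(σ_w² + σ_b²)/24) with df = 96 − 1 − 3 − 3 = 89. At CV 30%: √(2 × (0.0862 + 0.2231)/24) = 0.161, and exp(1.987 × 0.161) = 1.38, against 1.18 with the subject effect. Across the four CVs the factors are 1.34, 1.38, 1.42 and 1.52; at a between-person CV of 30% they are 1.23, 1.27, 1.32 and 1.43. This is an upper figure. The documents do not say which sequences are used. Four treatments allow 4! = 24 orders, and if nearly every participant had a different order, the sequence term would act almost as a subject term.

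**Dose.** The raw AUC ratio equals the bioavailability ratio times the dose ratio. If one product carried 20% less of a parent compound (assumed), equal bioavailability would give a raw ratio of 0.80, significant in 97%, 74%, 51% and 28% of trials at the four CVs. If D is constant within a product, dividing by D moves the ratio but leaves the interval width unchanged.

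**The case against.** The case for leaving this alone is substantial.

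- **The word carries no weight.** It sits in a duplicated eligibility rationale on an ethics form, and SAP 1.4 already states a difference aim. The products are deliberately contrasted: the procedures describe varieties chosen for phytochemical content, and there is a control beverage. This stands. A reader might infer that the trial plans an equivalence conclusion, or that a null result will be reported as one. No sentence says so, and none ties the word to a product pair.
- **Intervals are not ruled out.** A reader might take the protocol's statement that "study outcome data will only be provided as summarized group means and standard deviations" as barring confidence intervals. It answers a question about who will have access to the data, and it does not list statistical outputs; taken literally it would also bar the SAP's own F-tests. SAP 2.3 is output from a toy dataset of 15 subjects and two treatments, and its standard error already gives an additive interval: 1.917 ± 1.973 × 0.455, or 1.02 to 2.81. This stands too, but that interval is neither a ratio nor from a model with a subject term.
- **A subject effect may be intended.** SAP 1.4 names model (1.1) as its framework. No equation has that number, and the general model in 1.3 is the likely target. Even so, the models that 2.2 puts forward for analysis, and the code, omit the term, so adding it is a real change.
- **The size is assumed.** Only the sample size and design come from the documents. At a CV of 20% the problem is negligible with a subject-level model.

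**Conclusion.** The concern holds as a minor to moderate point. The eligibility clause conflicts with the stated purpose and the SAP, and without a margin, ratio or interval rule the planned analysis cannot establish bioequivalence. Taken alone that is a wording correction. What lifts it above clerical is that the proposed models, on raw AUC with no subject effect, are a weaker answer to the trial's comparative question than a log-scale, subject-level analysis of the same data.

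The actual size cannot be read from the documents. Under the stated assumptions it runs from negligible at a within-person CV of 20% to serious at 60%, where a 25% deficit would be missed in more than half of trials and equivalence could almost never be shown.

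**What to change.** 1. In both places in the eligibility text, replace bioequivalence with differences in bioavailability. The protocol title is marked closed; if it can no longer be amended, a clarifying sentence in SAP 1.4 serves.
2. In SAP 1.4 and 2.2, analyse AUC0-48, Cmax and dose-based bioavailability of the primary metabolites on the log scale. Include treatment, period and sequence effects and a random subject effect, following the general model in SAP 1.3. Amend models 2.1 and 2.2 and the code to match.
3. Report geometric mean ratios with 95% confidence intervals for the three contrasts among the blueberry products. State the D used for each product, and note that the bar is matched to a serving only on total phenolics.
4. Set a rule for zero values and for pre-dose background, which pulls raw AUC ratios towards 1. The planned pre-dose samples and the control make such a rule possible.
5. State that a non-significant test will not be read as equivalence. Any equivalence claim would need limits and a multiplicity rule fixed before concentration data are analysed.

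The cost is a few sentences, the rules in items 3 and 4, and nine ratios per primary metabolite (three contrasts by three parameters). No extra participants or samples are needed. The downside is a little more analysis, and that equivalence may prove unclaimable at this sample size.
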